3.3 Justification for the clinical investigation

Princess[®] VOLUME Lidocaine has recently been approved for the correction of deeper wrinkles and folds, augmentation or restoration of the volume of the face, remodeling of facial contours, and for medical reconstructive purposes in the treatment of, e.g., facial lipoatrophy, debilitating scars, or morphological asymmetry of the face. The approval was based on similarity with other dermal fillers, which showed a favourable risk-benefit ratio in these indications. The current clinical investigation is designed to support the approval by obtaining clinical data on the performance and safety of Princess[®] VOLUME Lidocaine for the correction of nasolabial folds.

A prospective, open label, non-comparative design was selected because it allows for the most efficient collection of clinical data on the investigational device, in a manner which is appropriate to address the purpose and objectives of the present investigation. In the absence of spontaneous improvement of nasolabial folds, it is reasonable to assume that the treatment effect can be adequately assessed by comparing the post-treatment observations versus baseline, eliminating the need for a control group.

The primary performance endpoints is based on evaluation using a validated 5-point scale for assessment of severity of nasolabial folds, the Nasolabial Folds Severity Rating Scale (NLF-SRS), and is set at 6 months after administration of the device to address the minimum required durability of effect. Follow-up is, however, extended to 9 months, to get additional information on long-term effects. Information on occurrence of pain will be primarily obtained by collection of AEs, with additional insight into pain intensity being obtained directly after the injection using a validated 11-point Numeric Pain Rating Scale (NRPS)¹⁶.

Up to 60 subjects will be included in this investigation to obtain 6-month effectiveness data in at least 40 subjects. This sample size is arbitrarily selected, based on usual size of post-market clinical investigations, and is considered sufficient to provide robust estimations on performance and safety parameters in the study population.

4 Risks and benefits of the investigational device and clinical investigation

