6.1.1 Primary performance endpoints

The performance of the investigational device will be evaluated using the following primary endpoints (justification is provided in Section 3.3):

- The average change versus baseline (Day 0) in the NLF-SRS grade of nasolabial folds at Week 24 as evaluated by the investigator.
- The proportion of subjects with the NLF-SRS grade reduced by ≥1 point versus baseline at Week 24

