6.1.4.2 Week 2 Visit (Visit 2)

The following assessments will be performed 2 weeks (± 2 days) after Visit 1:

- Photography (Optional)
- Touch-up treatment (optional)
- Pain assessment (only if Touch-up treatment performed)
- Adverse events
- Concomitant medication

6.1.4.3 Week 4 (Visit 3), Week 24 (Visit 4) and Week 36 (Visit 5) Visits

The following assessments will be performed respectively 4 weeks (\pm 4 days), 24 weeks (\pm 7 days) and 36 weeks (\pm 7 days) after Visit 1:

- Photography
- NLF-SRS grading of nasolabial folds
- GAIS assessment
- Subject satisfaction
- Adverse events
- Concomitant medication

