6.2.4 Touch-up treatment

A Touch-up treatment may be performed at the Week 2 visit at the investigator's discretion, if correction is not deemed satisfactory after the first injection. It will be documented in the CRF with the same level of details as the initial treatment.

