3.6 Visit Terminology

The following visit notation will be used for table, listing, and graph presentation:

Visit no.	Notation used on the case report form	Notation used for TLG		
1	VISIT 1 (Day 0)	Baseline		
2	VISIT 2 (Week 2 ± 2 days)	Week 2		
3	VISIT 3 (Week 4 ± 4 days)	Week 4		
4	VISIT 4 (Week 24 ± 7 days)	Week 24		
5	VISIT 5 (Week 36 ± 7 days)	Week 36		

4 Statistical Evaluation

Continuous variables will be presented using number of subjects with non-missing observations (N), mean, standard deviation (SD), median, minimum (min), maximum (max), 1st quartile and 3rd quartile. In general, min and max will be presented to the same level of precision as the raw data; means and medians, SD, and quartiles will be presented to one further decimal place. Categorical variables will be presented by frequency tables, using number and percentage. Percentages will be presented to one decimal place.

Baseline is defined as the measurements taken on Day 0 before treatment.

For each subject two facial folds (right and left) are rated per time point and grades (NLF-SRS and GAIS). As no great difference between those two folds is expected, the mean grade of both measurements will be calculated per time point.

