4.3.1 Analysis of Primary Performance Endpoints

The primary performance endpoints will be analyzed for the ITT, modITT and PP.

The change from baseline in the average grade of NLF-SRS as assessed by the investigator to Week 24 will be summarized with descriptive statistics for continuous variables. Additionally, the 95% confidence intervals of the mean will be given.

The proportion of subjects with the average grade of NLF-SRS as assessed by the investigator reduced by ≥1 point versus baseline will be summarized with frequency tables at Week 24.

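### Do visits at Weeks 24 and 36, counted from the first injection, overstate durability that the protocol describes as 6 and 9 months?

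*Protocol*

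**What the plan says.** Protocol 3.3 explains the timing of the primary endpoint: it "is set at 6 months after administration of the device to address the minimum required durability of effect". On the later visit it adds: "Follow-up is, however, extended to 9 months, to get additional information on long-term effects". The synopsis, Protocol 6.3.1 and the SAP paragraph on study duration also give 9 months per subject.

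The operative text uses weeks. The first primary endpoint in Protocol 6.1.1 is "The average change versus baseline (Day 0) in the NLF-SRS grade of nasolabial folds at Week 24 as evaluated by the investigator", and the responder endpoint has the same time point. SAP 3.6 lists "VISIT 4 (Week 24 ± 7 days") and "VISIT 5 (Week 36 ± 7 days"). Protocol 6.1.4.3 counts these visits from Visit 1.

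Protocol 6.2.4 allows a second session: "A Touch-up treatment may be performed at the Week 2 visit at the investigator's discretion". It is given when the first correction is judged unsatisfactory. SAP 4.3.1 pools all subjects: "The primary performance endpoints will be analyzed for the ITT, modITT and PP". The body of the SAP has no performance table by touch-up status or by time since last injection.

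**The concern.** The rationale appeals to a minimum required duration, so a visit that falls short of that duration looks like weak evidence for it. Read in calendar months, no visit inside its window reaches 6 or 9 months. A subject touched up around Day 14 has received more gel, and received it later, but is assessed on the same dates as a subject treated once.

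Protocol 2.1 describes a gel that is absorbed over time. A more recent last injection would, other things equal, favour response. If pooled results were then presented as 6-month and 9-month durability, the stated interval would be too long, and readers could not tell how much of the response came from a single session.

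**Working it through.** **Inputs.** Week 24 ± 7 days and Week 36 ± 7 days from Visit 1 (Protocol 6.1.4.3, SAP 3.6); touch-up at Week 2 ± 2 days, i.e. Day 12 to 16 (Protocol 6.1.4.2); 6 and 9 months (Protocol 3.3). No month-to-week conversion and no expected touch-up rate is stated.

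**1. Reproducing the plan's figures.** With 28-day months, 6 × 28 = 168 = 24 × 7 and 9 × 28 = 252 = 36 × 7. The month and week statements then agree exactly, counted from Day 0. No longer month reproduces them.

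**2. Calendar reading.** Six calendar months span 181 to 184 days and nine span 273 to 276, depending on the start date. With a mean month of 365.25/12 = 30.44 days they are 182.6 and 273.9 days.

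| Visit | Days from Day 0 | Mean months | Nominal shortfall | Shortfall of latest in-window visit against shortest calendar span |
|---|---|---|---|---|
| Week 24 | 161–175 (168) | 5.29–5.75 (5.52) | 182.6 − 168 = 14.6 d | 181 − 175 = 6 d |
| Week 36 | 245–259 (252) | 8.05–8.51 (8.28) | 273.9 − 252 = 21.9 d | 273 − 259 = 14 d |

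**3. Time since a touch-up.** Subtract Day 12 to 16 from the visit day.

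- Week 24: 161 − 16 = 145 to 175 − 12 = 163 days (4.76 to 5.36 mean months); nominal 168 − 14 = 154.
- Week 36: 245 − 16 = 229 to 259 − 12 = 247 days (7.52 to 8.11 mean months); nominal 252 − 14 = 238.
- In 28-day months these are still only 5.18 to 5.82 and 8.18 to 8.82, so this part does not depend on the definition of a month.

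**4. Effect on the group average.** If a share f of subjects is touched up, mean time since last injection at the nominal Week 24 visit is 168 − 14f days. With f assumed at 0, 25, 50 and 100%, that is 168, 164.5, 161 and 154 days. Even at 50% the average only reaches the early edge of the permitted window for a subject treated once.

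**5. Are the months a separate claim?** Protocol 3.3 wants six-month data in at least 40 of up to 60 subjects. Protocol 6.3.1 and 7.1 state the same target as Week 24 data in at least 40 of up to 60. These are one target in two units. The tables, listings and graphs take their visit labels from SAP 3.6, which are in weeks.

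**6. Precision.** The planned half-width 1.96 × √(0.9 × 0.1/n) gives 0.076 at n = 60 and 0.093 at n = 40, as the SAP states. Nothing above alters it.

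**The case for a change.** The strongest case for a change is this. The shortfall always runs toward a longer described duration, and the rationale concerns a minimum. The touch-up gap holds under any month convention. The device supply in Protocol 6.2.7 suggests that touch-up was provided for on a large scale: 60 subjects × 2 folds × 0.9 mL = 108 mL, or 120 one-mL syringes at two per subject, against about 300 units planned. The remaining 180 units come to three per subject. Injection dates and touch-up details are already recorded (Protocol 6.2.3 and 6.2.4), so a split table would cost little.

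The arithmetic stands, and so does the fact that the SAP body has no such split. Its table specifications sit in an Appendix A that is not in the text reviewed, so the absence can be stated only for the body. The rest carries less weight:

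- A supply allowance is not a touch-up rate and may include overage.
- The direction of any bias is open. A fresher and larger total injection could favour response, but touched-up subjects are selected for poor first correction, which could work the other way.
- For the same reason, a split by touch-up compares groups formed by early response, within 40 to 60 subjects. It would be descriptive and easily misread as an effect of touch-up.
- Protocol 7.4 already lists and summarises touch-up occurrence and amount. An analyst who wants days since last injection can derive them without new data.

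**Conclusion.** The concern does not call for a change. The mismatch is one of wording in the rationale and duration statements: about 15 days at Week 24 and 22 days at Week 36 in mean calendar months, and none in 28-day months. For touched-up subjects, the time from last injection at the nominal visits is about 29 and 36 days short of 6 and 9 calendar months. Because endpoints, visit labels and analyses are all in weeks, results reported as planned carry the correct time from first treatment. For 9 months, Protocol 3.3 promises only further information, not a demonstrated duration.

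Pooling is a fair choice. The synopsis and the SAP define treatment as one application with an optional touch-up after two weeks, and Protocol 6.4.12 describes a study meant to resemble ordinary practice. Performance of that course, timed from its start, is a coherent target. Time since last injection is a different question.

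That durability is overstated in the fold grades is not shown, since the documents give neither a touch-up rate nor a rate of loss. The proposed split would alter no estimate, interval or sample size. This conclusion assumes that the report keeps the week labels of SAP 3.6.

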4.1 Anticipated clinical benefits

The treatment with Princess[®] VOLUME Lidocaine may remove or reduce a distressing aesthetic defect in subjects with moderate-to-severe nasolabial folds, thereby improving their psychological and social wellbeing. This is achieved by a minimally invasive procedure with a short downtime, which results in an immediate and long-lasting effect, persisting for 6-12 months.

4.2 Anticipated adverse device effects

The safety profile of BDDE-cross-linked hyaluronic acid dermal fillers, with or without lidocaine, is well established. In general, these devices are well tolerated and safe, with a low frequency of side effects¹⁷. Adverse effects that have been observed with devices similar to Princess[®] VOLUME Lidocaine are summarized in Table 2, on the following page.

Currently, there are no human safety data on Princess[®] VOLUME Lidocaine. There is, however, a considerable experience with Princess[®] VOLUME, which is essentially the same device, just without lidocaine. Almost 2 million (1,971,500) units of Princess[®] VOLUME (without lidocaine) have been sold worldwide from 2009 up to the end of 2015, and during the same period there were only 38 spontaneous ADE reports. Among these, 22 were cases of oedema, redness, inflammation, pain or swelling, which are commonly observed with any dermal filler. The remaining 16 comprised cases of nodules, lumps, burning, discoloration and a single report of an allergic reaction, all of which resolved shortly after occurrence⁸.

Table 2. Adverse effects of cross-linked hyaluronic acid dermal fillers (with or without lidocaine)

Common	Rare	Very rare
 Redness, erythema Swelling, oedema Pain, itching, burning, discomfort Tenderness Bleeding Bruising, hematoma 	 Hypersensitivity, angioedema Infection, abscess Herpes reactivation Irritation, inflammation, granuloma Malar oedema Implant visibility, nodules, beading, lumpiness, implant-site mass Firmness, induration Discoloration, dispigmentation, puncture marks Paresthesia, numbness Implant migration Scar sarcoidosis Scleromyxedema Teleangiectasia (generalized) Vasculitis cutaneous Vasospasm Vasovagal reaction during injection 	 Vascular compromise or arterial occlusion (typically presented as immediate skin blanching, followed by a Livedoid pattern, discoloration or necrosis) Retinal artery occlusion, vision loss Necrosis

Common AEs like swelling, redness, tenderness, pain and bruising are typically mild in severity and usually resolve within 1-2 days after injection; resolution of bruising may take a little bit longer. Discomfort and pain may be reduced or prevented by application of ice before the injection or local anaesthesia. Redness, swelling and bruising may be prevented or alleviated by application of ice-packs for 5-10 minutes after the injection.

Additional information on AEs, especially serious events like arterial occlusion and necrosis is provided in the IB.

In case impending tissue necrosis, which may occur with any dermal filler, a recent consensus statement on the treatment of hyaluronic acid filler-induced impending necrosis recommends immediate treatment with high doses of hyaluronidase (e.g., at least 200 units of equivalent), followed by warm compress, vigorous massage and topical nitroglycerin paste. If no improvement is seen within 60 minutes, additional quantities of hyaluronidase should be injected (3-4 cycles in total). An oral aspirin regimen (e.g., 650 mg per day) should help prevent further clot formation. Daily follow-up is advised. If no improvement or progression of necrosis is observed, the above regimen of hyaluronidase, nitroglycerin paste and aspirin should be repeated daily, typically for 2-3 days¹⁸.

4.3 **Possible interactions with concomitant medical treatments**

No studies on drug interactions with Princess[®] VOLUME Lidocaine have been conducted in humans.

Anticoagulant and antiplatelet drugs may increase the risk of bleeding or bruising, so the subject should be asked about use of such medications, and the prescribing physician should be consulted to appropriately assess the risk level.

Sodium hyaluronate is incompatible with quaternary ammonium compounds such as benzalkonium chloride solutions. The device should never be placed in contact with these substances or with medical-surgical instruments that have been in contact with these substances.

4.4 Risk mitigation strategy

The risks will be mitigated by careful selection of the subjects and exclusion of those who may have an increased risk of developing certain types of AEs (see Section 6.3.5), proper injection technique (described in Section 6.2.2), appropriate training of the investigators to ensure correct application of the device, and regular follow-up visits over the following 9 months, which will allow for timely recognition and management of potential AEs. Furthermore, the subjects will be instructed to immediately contact the investigator in case of occurrence of any AE between the scheduled visits.

4.5 Risk-to-benefit rationale

Hyaluronic acid-based dermal fillers, such as Princess[®] VOLUME Lidocaine, are generally considered very safe and effective, and have been widely used for soft tissue augmentation worldwide. There is also no scientific evidence demonstrating adverse events of fillers or hyaluronidase in pregnant women. Observed adverse effects are mainly related to the injection procedure, are transient and mostly mild. While few serious adverse effects have been reported, these are very rare and not expected to occur when the device is correctly applied. This is supported by a remarkable safety track record of Princess[®] VOLUME (without lidocaine), with few ADEs reported among almost 2 million units sold since 2009, combined with favorable safety data from one clinical trial.

The performance and safety of lidocaine-containing hyaluronic acid dermal fillers for correction of nasolabial folds have been well documented in medical literature, and Princess[®] VOLUME Lidocaine has been approved for use in this indication. Considering the potential benefits of correction, in particular the immediate and long lasting improvement of distressing aesthetic defect, and the low risk of the treatment when used appropriately by an experienced user, the benefits clearly outweigh the potential risks.

5 Objectives and hypotheses of the clinical investigation

5.1 Objectives

The objectives of this post-market clinical follow-up investigation are:

- To evaluate the performance of Princess[®] VOLUME Lidocaine for the correction of nasolabial folds.
- To evaluate the safety of Princess[®] VOLUME Lidocaine when used for correction of nasolabial folds.

5.2 Hypotheses

This is a non-comparative study and does not entail formal hypothesis testing.

5.3 Claims and intended performance of the investigational that are to be verified

Princess[®] VOLUME Lidocaine has recently been approved for the correction of deeper wrinkles and folds, and other indications typical for hyaluronic acid dermal fillers. The approval was based on clinical experience with similar devices and the present investigation is undertaken to support these claims.

5.4 Risks and anticipated adverse device effects that are to be assessed

The safety profile of lidocaine-containing hyaluronic acid dermal fillers is well established. Based on the equivalence of Princess[®] VOLUME Lidocaine with these products and available non-clinical safety data, it is anticipated that it will share the same safety profile, described in Section 4.2. All AEs and device deficiencies occurring during the investigation will be collected and reported.

6 Design of the clinical investigation

6.1 Design description

The present investigation is designed as a prospective, open label, multicenter, post-market study. As justified in Section 3.3, this type of design is considered appropriate in view of the purpose and objectives of the study.

The investigation will consist of five visits: the baseline (Day 0) visit, which will entail informed consent, screening assessments, the treatment, and early post-treatment assessments, and follow-up visits 2,

4, 24 and 36 weeks after the treatment. Procedures to be performed at each visit are specified in Table 1. Schedule of procedures and events, which is located on page 8 and in section 6.1.4.

6.1.1 Primary performance endpoints

The performance of the investigational device will be evaluated using the following primary endpoints (justification is provided in Section 3.3):

- The average change versus baseline (Day 0) in the NLF-SRS grade of nasolabial folds at Week 24 as evaluated by the investigator.
- The proportion of subjects with the NLF-SRS grade reduced by ≥1 point versus baseline at Week 24

6.1.2 Secondary performance endpoints

- The average change versus baseline in the NLF-SRS grade at Week 4 and Week 36 as evaluated by the investigator.
- The proportion of subjects with the NLF-SRS grade reduced by ≥1 point versus baseline at Week 4 and Week 36
- The proportion of subjects with aesthetic improvement at Week 4, Week 24 and Week 36, as evaluated by the investigator using the Global Aesthetic Improvement Scale (GAIS)
- Subjects' satisfaction with aesthetic outcome of the treatment at Week 4, Week 24 and Week 36, as evaluated by the subject
- The average pain intensity during and after the treatment, as evaluated by the subject using an 11-point Numeric Pain Rating Scale (NPRS) immediately after the last injection and 15 min. thereafter, respectively.
- The proportion of subjects with the NLF-SRS grade reduced by ≥1 point versus baseline at Week 24 as evaluated by the independent reviewer of photographs.

6.1.3 Safety endpoints

The safety of the investigational device will be evaluated using the following endpoint:

• Occurrence and frequency of adverse events

6.1.4 Schedule of procedures and events

6.1.4.1 Baseline Visit (Visit 1)

After written informed consent is obtained, the following assessments will be performed during Baseline Visit at Day 0:

- Demographic data collection
- Medical history (including information on prior facial aestetic or surgical procedures)
- Prior medication
- Urine pregnancy test (in women of child-bearing potential)
- Photography
- Evaluation of inclusion and exclusion criteria
- NLF-SRS grading of nasolabial folds
- Treatment
- Pain assessment
- Adverse events
- Concomitant medication

6.1.4.2 Week 2 Visit (Visit 2)

The following assessments will be performed 2 weeks (± 2 days) after Visit 1:

- Photography (Optional)
- Touch-up treatment (optional)
- Pain assessment (only if Touch-up treatment performed)
- Adverse events
- Concomitant medication

6.1.4.3 Week 4 (Visit 3), Week 24 (Visit 4) and Week 36 (Visit 5) Visits

The following assessments will be performed respectively 4 weeks (\pm 4 days), 24 weeks (\pm 7 days) and 36 weeks (\pm 7 days) after Visit 1:

- Photography
- NLF-SRS grading of nasolabial folds
- GAIS assessment
- Subject satisfaction
- Adverse events
- Concomitant medication

6.1.5 Replacement of subjects

Subjects withdrawn from the investigation or lost for follow-up will not be replaced.

6.2 Investigational device

6.2.1 Packaging, labelling and storage

The investigational device will be obtained from the commercial manufacturing batch.

Each device will be provided in a folding box containing one syringe prefilled with 1.0 mL of the injectable gel implant, two 27G $\frac{1}{2}$ " disposable sterile needles and a product leaflet. A set of two labels showing the batch number is situated at the bottom of the box. One of these labels should be attached to the subject's file and the other must be given to the subject to ensure traceability of the device.

An additional label, indicating that the device is exclusively for use in a clinical investigation, will be placed on the outer commercial package of each investigational device, if required by national regulations.

The investigational device must be stored in the original box, at 2-25°C in a dry place, protected from light, heat and frost. The investigator must ensure that upon receipt of the investigational device and other study supplies, these are kept in an appropriate and secure location, with access limited to authorized individuals.

